#### 6.5.4 Missing Data

Step count and MVPA data may be missing for any day if the Fitbit is not used or not synced. To prevent potential downward bias from very low minutes per day, we will ignore days in which fewer than 1000 steps are recorded, as this likely represents a failure to capture actual activity.(Rowe, Mahar et al. 2004, Patel, Benjamin et al. 2017) We will use multiple imputation for missing data or days with fewer than 1000 steps recorded, and results will be combined using standard rules.(Rubin 1987, Allison 2002) Predictors will include baseline daily minutes in MVPA, experimental condition, week in study after baseline (1-12), calendar month, and an indicator variable for weekday or weekend.(Patel, Benjamin et al. 2017) We will perform sensitivity analyses using all collected data without multiple imputation, including or excluding days with fewer than 1000 steps. Of note, mixed effects models allow for handling of incomplete and unbalanced data, making possible an intention-to-treat approach using the missing at random assumption. To minimize confounding for secondary outcomes, in a sensitivity analysis, subjects who start a new medication that may alter weight (including metformin, insulin, or glucagon-like peptide-1 receptor agonists) after visit 1 will have visit 5 weight, waist circumference, and laboratory measurements censored.

As an exploratory analysis, for days with missing Fitbit data, we will use participant-reported step count data recorded by their smartphones (sent via screenshot once weekly via text message to Way to Health).

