### **2.2 Secondary Objectives**

The secondary objectives are to:

- Determine the main and interactive effects of the four intervention components on:
  - Daily step count
  - body mass index Z-score
  - hemoglobin A1c
  - fasting insulin
  - fasting plasma glucose
  - fasting triglycerides, LDL, and HDL
  - AST, ALT
- Explore participant-reported intervention acceptability, including constructs of burden, perceived effectiveness, and impact on self-efficacy
- Assess baseline and intervention-related changes in intrinsic versus extrinsic motivation to pursue physical activity
- Assess the association between baseline delay discounting tendency and baseline and change in MVPA and step count
- Assess the correlation between Fitbit-measured physical activity and smartphone-measured physical activity

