## 4.3 Run-In and Randomization

### 4.3.1 2-Week Run-In

- Participant wears Fitbit daily during waking hours and syncs daily with smartphone
- Daily text message reminder sent to participant
- On day 15, study team will evaluate MVPA during days 8-14
  - Exclude from intervention if mean > 30 minutes/day or if < 4 days with evaluable Fitbit data
- Calculate mean daily step count during days 8-14, to provide to participant for reference

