### 6.4 Control of Bias and Confounding

Potentially eligible subjects will be stratified by sex and age (13-18, 19-22), and an equal number of participants will be contacted per group until recruitment goals are reached or all potentially eligible subjects in a category are enrolled or decline to participate.

Multivariable models will adjust for covariates including age, sex, race, ethnicity, disease type (prediabetes versus diabetes), baseline laboratory values, anthropometrics (e.g. BMI-Z), and baseline activity level. The distribution of measured motivation characteristics and delay discounting tendencies will be assessed across intervention components (e.g., proportion with high measures of intrinsic motivation among those randomized to loss-framed versus those randomized gain-framed incentives) will be assessed. If imbalanced across components, these measures will be included in multivariable models.

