**Table 1. Analysis plan**

Outcome	Analysis/statistical test
MVPA min/day: baseline vs 6 and 12 weeks ( primary outcome )	Mean/SD or median/IQR, ANOVA/ANCOVA
MVPA min/day: baseline vs 6 and 12 weeks	% of days with $\geq 60$ min/day, Fisher's exact test
MVPA min/day: average per week of intervention	% of days with $\geq 60$ min/day, Fisher's exact test
Steps/day: baseline (2 nd -week of run-in) versus 6 weeks and 12 weeks	Mean/SD or median/IQR, ANOVA/ANCOVA
Steps/day: baseline (2 nd -week of run-in) versus 6 weeks and 12 weeks	% of days with $\geq 10,000$ steps/day, Fisher's exact test
Steps/day: average per week of intervention	% of days with $\geq 10,000$ steps/day, Fisher's exact test
Body mass index Z-score	Mean/SD or median/IQR, ANOVA/ANCOVA
Hemoglobin A1c, insulin, glucose, triglycerides, LDL, HDL, AST, ALT	Mean/SD or median/IQR, ANOVA/ANCOVA
Hemoglobin A1c	% $<5.7\%$ , $5.7\text{-}6.4\%$ , $\geq 6.5\%$ , Fisher's exact test
Healthy Eating Index	Mean/SD or median/IQR, ANCOVA covariate, Pearson/Spearman correlation with demographic variables
Measure of delay discounting, k , derived from MCQ	Mean/SD or median/IQR, ANCOVA covariate (visit 1 measure), Pearson/Spearman correlation with demographic variables, paired t-test or Wilcoxon signed rank test to assess whether baseline and follow-up measures differ
Relative Autonomy Index (RAI) from BREQ-3	Mean/SD or median/IQR, ANCOVA covariate (visit 1 measure), Pearson/Spearman correlation with demographic variables, ANOVA/ANCOVA to assess change from visit 1 to 5 by experimental factor
PACE+: number of days with at least 60 minutes of activity per day in (a) past 7 days and (b) typical week	Mean/SD or median/IQR, Pearson/Spearman correlation with demographic variables and with number of days with MVPA $\geq 60$ minutes at baseline and week 12
Steps/week on smartphone activity tracker	Pearson/Spearman correlation with Fitbit-measured steps/week

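### The imputation model for missing Fitbit days omits delay discounting and the Relative Autonomy Index, so their baseline-adjusted associations with MVPA and steps shrink by roughly the imputed share if estimated on imputed data

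*Combined protocol and SAP*

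**What the plan says.** Section 6.5.4 states "We will use multiple imputation for missing data or days with fewer than 1000 steps recorded". The named predictors are "Predictors will include baseline daily minutes in MVPA, experimental condition, week in study after baseline (1-12), calendar month" "and an indicator variable for weekday or weekend". The section also plans sensitivity analyses on all collected data without imputation, and notes that mixed models can handle incomplete data under missing at random.

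Section 2.2 lists among the secondary objectives: "Assess the association between baseline delay discounting tendency and baseline and change in MVPA and step count". In Table 1 (analysis plan), the row for k reads "ANCOVA covariate (visit 1 measure), Pearson/Spearman correlation with demographic variables, paired t-test or Wilcoxon signed rank test", and the RAI row gives the Visit 1 value the same covariate role. Section 6.3 classes k and RAI as exploratory measures to be used as covariates. Section 6.4 says "Multivariable models will adjust for covariates including age, sex, race, ethnicity, disease type (prediabetes versus diabetes), baseline laboratory values", then continues with anthropometrics and baseline activity level; it adds motivation and delay discounting if they are imbalanced across components.

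Section 6.5.3 will compare Fitbit adherence by k, RAI, disease type and demographics. Section 4.3.1 has staff "Calculate mean daily step count during days 8-14, to provide to participant for reference", so baseline steps exist for every randomised participant.

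**The concern.** The models that use k and RAI contain variables that the listed imputation model does not. A day imputed without k has no association with k beyond what the listed predictors carry. Experimental condition is randomised and the calendar terms have no designed link to k, so in practice only baseline MVPA can carry any. Mixing such days with observed days dilutes the k slope even when data are missing at random. At stake is the size of, and the power for, a stated secondary objective, and likewise the RAI covariate result. The plan itself treats k and RAI as possible correlates of Fitbit wear, which is a further reason to condition on them.

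**Working it through.** **The plan's own figures.** The documents give no power for the k association and no expected share of missing days. Section 6.6 gives 15% dropout: 75 × 0.85 = 63.75, about 64 evaluable. Its power of 0.84 (15 minutes, SD 20, N = 64, so 32 per level) reproduces: noncentrality = 15 / (20 × √(2/32)) = 15/5 = 3.0, giving 0.84 on 62 df. That figure concerns factor effects, not k.

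**1. Baseline-adjusted slope.** Let week-12 MVPA be Y = a + ρB + βk + error, with B baseline MVPA and k in SD units. Observed days have adjusted slope β. Imputed days, drawn from the listed predictors, have adjusted slope 0. With share f imputed:

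adjusted slope = (1 − f) × β + f × 0 = (1 − f)β.

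At f = 0.15 this is 0.85β, a loss of 15%. Combining imputations averages the estimates and does not undo the loss. The same algebra applies to RAI.

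**2. Small-sample addition.** With condition entered as 16 levels, each cell mean comes from very few completers and uses up information. For whole-person dropout the ratio becomes about (64 − 16)/(75 − 16) = 48/59 = 0.81, a loss of 19%. Two simulations with condition in the imputation gave 0.81 and 0.82. Hence the range of 15-19%.

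**3. Other missing shares (all assumed).** Ratio of the imputed-data to the full-data adjusted slope, imputing from baseline MVPA alone; assumed k slope −4 min/day per SD, between-person SD 12, day-to-day SD 18, ρ = 0.6:

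| Share imputed | Listed predictors | Own observed days also used |
|---|---|---|
| 5% | 0.95 | 0.99 |
| 10% | 0.90 | 0.97 |
| 20% | 0.79 | 0.93 |
| 30% | 0.71 | 0.90 |
| 40% | 0.60 | 0.85 |

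With k in the imputation model the ratio is 1.00-1.01 throughout. When the whole week is missing, own days cannot help: 0.90, 0.80 and 0.60 at 10%, 20% and 40%. If missingness rises with k (log-odds 0.7 per SD, about 22% missing), the ratio is 0.72-0.73.

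A second simulation (N = 75, 16 conditions) took 15% dropout plus 0%, 10%, 20% or 30% of the remaining days, so 15%, 24%, 32% or 40% imputed. It gave 0.81, 0.73, 0.65 and 0.56, close to 0.81 × (1 − extra share) = 0.81, 0.73, 0.65, 0.57. Adding k restored 1.00.

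**4. Unadjusted change score.** Let γ be the slope of B on k, and δ = Cov(k, B)/Var(B). The true change slope is ργ + β − γ. On imputed days it is (ρ + βδ)γ − γ. Take ρ = 0.6, γ = −4 and residual baseline SD 12, so Var(B) = 144 + 16 = 160 and δ = −4/160 = −0.025.

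- β = −1.6: true slope 0; imputed days 0.64 × (−4) + 4 = 1.44. The mixture is 0.29 at f = 20% and 0.58 at 40% (simulated: 0.27, 0.60).
- β = −1.0: true slope 0.60; imputed days 0.625 × (−4) + 4 = 1.50. The mixture is 0.78 and 0.96 (simulated: 0.83, 0.96). This bias is away from zero.
- β = −4: true slope −2.40; imputed days 0.70 × (−4) + 4 = 1.20. The mixture is −1.68 and −0.96 (simulated: −1.64, −0.95). This bias is towards zero.

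**5. Steps.** With 28% imputed and assumed correlations of 0.7 (baseline MVPA with baseline steps) and 0.6 (baseline with week-12 steps), adding baseline steps took the empirical SD of a factor coefficient from 0.128 to 0.123: 0.123/0.128 = 0.96, a gain of about 4%.

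**The case against.** - **The list is not closed.** Its wording permits further predictors. True, but it is the only specification given, and an analyst who follows it omits k.
- **The k objective may not use imputed data.** Section 6.5.4 plans unimputed sensitivity analyses and section 6.5.1 plans mixed models; run on observed days, neither carries this dilution. This stands in part: the plan assigns the objective to no dataset, and Table 1 gives no separate test of k against change. The conclusion is therefore conditional, but nothing exempts the objective from imputation.
- **Own observed days would shrink the loss.** They would, to about 1-15% for partly observed weeks. They are not listed, and they do not help a participant with no week-12 data.
- **Stronger readings a reader might infer.** One is that the k association must be biased towards zero. That holds for the baseline-adjusted slope only (step 4). Another is that every omitted variable pulls the k slope down. Only omitting k does so; omitting RAI affects the RAI slope, and omitting baseline steps costs mainly a little precision. A third is that no section 6.4 covariate is in the imputation, but baseline MVPA is.
- **Power losses.** A simulated fall from 0.81 to 0.67 with dropout alone rests on a slope of 6 min/day per SD of log k, which has no source in the documents. It is illustrative only.

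**Conclusion.** The concern holds in conditional form. If the k objective is analysed on data imputed as section 6.5.4 lists, the baseline-adjusted k slope is understated by roughly the imputed share: about 15-19% when only the planned 15% dropout is imputed. The RAI slope suffers likewise when RAI is omitted. Larger losses need missing-day shares that the documents do not give, and the plan does not say whether dropouts are imputed at all. For an unadjusted change score the direction is not fixed.

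A reader might infer that the trial's main results are affected. The documents do not support that: experimental condition is in the imputation model, so factor effects on MVPA, including the primary endpoint, are not attenuated by this mechanism. The change is worth making because a stated secondary objective is exposed and the remedy is cheap.

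**What to change.** In section 6.5.4, do one of the following and say which dataset serves the k and RAI associations:

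- Add Visit 1 log k and RAI to the imputation predictors, with the limited set of section 6.4 covariates actually used in that outcome's model. When steps are imputed, also use baseline daily steps from days 8-14 (a minor precision gain).
- Or state that the k and RAI associations are estimated from observed days without imputation, for example in the mixed model.

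Requiring every section 6.4 covariate is not advisable: the list is open-ended, these are person-level predictors, and only 64-75 participants must also support a 16-level condition term. The cost is a sentence or two and a slightly larger imputation model. All the variables are already collected at Visit 1 or in the run-in.

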#### 6.6 Sample Size and Power

To determine sample size, the MOST R package (FactorialPowerPlan) was used.(Collins, Huang et al. 2017) Using a sample size of 64, 4 factors (n=16/factor, n=4/experimental condition), and two-sided alpha = 0.05, we will have at least 80% power to detect a 15-minute change in MVPA assuming a standard deviation of 20 minutes(Kriska, Delahanty et al. 2013) (**Table 2**). To allow for 64 evaluable subjects, we will recruit 75 AYA (anticipated dropout rate of 15%). In 2020, the Children's Hospital of Pittsburgh Division of Pediatric Endocrinology, Metabolism, and Diabetes followed approximately 2200 patients, approximately 10% (~220) of whom have type 2 diabetes. The vast majority of youth with type 2 diabetes are in the adolescent age range that will be targeted in this intervention. In addition, a variable number of youth with prediabetes are seen by the Division. Based on this, a total sample size of 75 is feasible to enroll over the planned study period. For secondary outcomes including BMI Z-score, labs, and Healthy Eating Index, using a sample size of 64, 4 factors, and two-sided alpha = 0.05, we will have at least 80% power to detect a standardized regression coefficient of 0.36.

**Table 2.** Effect size and power estimates (N=64)

Δ	SD	Effect size	α	Power
15	20	0.38	0.05	0.84
15	20	0.38	0.1	0.91

-	-	0.36	0.05	0.80
-	-	0.32	0.1	0.80

## 7 SAFETY MANAGEMENT

### 7.1 Clinical Adverse Events

Clinical adverse events (AEs) will be monitored throughout the study.

### 7.2 Adverse Event Reporting

Since the study procedures are not greater than minimal risk, serious adverse events (SAEs) are not expected. If any unanticipated problems related to the research involving risks to subjects or others happen during the course of this study (including SAEs) they will be reported to the IRB in accordance with institutional guidelines. AEs that are not serious but that are notable and could involve risks to subjects will be summarized in narrative or other format and submitted to the IRB at the time of continuing review.

The relationship of each SAE to the study intervention will be characterized using one of the following terms in accordance with IRB Guidelines: definitely, probably, possibly, unlikely or unrelated.

### 7.3 IRB/IEC Notification of SAEs and Other Unanticipated Problems

The Investigator will promptly notify the IRB of all on-site unanticipated, serious Adverse Events that are related to the research activity. Other unanticipated problems related to the research involving risk to subjects or others will also be reported promptly. Written reports will be filed using the electronic IRB system and in accordance with the timeline below. External SAEs that are both unexpected and related to the study intervention will be reported promptly after the investigator receives the report.

Type of Unanticipated Problem	Initial Notification (Phone, Email, Fax)	Written Report
Internal (on-site) SAEs Death or Life Threatening	24 hours	Within 2 calendar days
Internal (on-site) SAEs All other SAEs	7 days	Within 7 business days
Unanticipated Problems Related to Research	7 days	Within 7 business days
All other AEs	N/A	Brief Summary of important AEs may be reported at time of continuing review

#### 7.3.1 Follow-up report

If an SAE has not resolved at the time of the initial report and new information arises that changes the investigator's assessment of the event, a follow-up report including all relevant new or reassessed information (e.g., concomitant medication, medical history) will be submitted to the IRB. The investigator will be responsible for ensuring that all SAE are followed until either resolved or stable.

### 7.4 Investigator Reporting of a Serious Adverse Event to Sponsor

Reporting will be consistent with National Institutes of Health requirements.

## **7.5 Medical Emergencies**

Medical emergencies that might develop during the course of the study at PCTRCC will be referred to the CHP emergency room. Medical emergencies that might develop during the course of the study during the at-home intervention will be referred to local emergency medical services.

## 8 STUDY ADMINISTRATION

### 8.1 Treatment Assignment Methods

#### 8.1.1 Randomization

The Way to Health platform will be used to generate random sequences to assign eligible participants to one of sixteen experimental conditions. We will use a block randomization approach so that we will have 3-5 participants randomized to each study condition. Demographic and clinical characteristics will be assessed at baseline. If there are differences with respect to key covariates (e.g., age, sex, baseline activity level) across component levels at baseline we will consider including those variables as covariates in our statistical models.

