## 6.5 Statistical Methods

### 6.5.1 Analysis of Primary and Secondary Outcomes of Interest

Descriptive and visual statistics: Demographic and clinical characteristics of subjects will be described using summary statistics, including means, standard deviations, medians, and ranges for continuous variables, and frequencies and percentages of participants for categorical variables. Data will be assessed for outliers. Scatter plots and box plots will be used to examine the relationship between independent (e.g. individual characteristics such as age, prediabetes versus T2D, race/ethnicity; as well as component level, such as gain versus loss-framed incentives) and dependent variables. Line plots will be generated for the primary outcome of daily MVPA, with one line per subject and an overall trend line. Longitudinal data will be summarized by factor level (e.g. loss-framed versus gain-framed incentives). Statistical analyses will be conducted using Stata 17 (StataCorp, College Station, TX) or R: A language and environment for statistical computing (R Corp Team, Vienna, Austria). The significance level for two-sided hypothesis testing will be set at 0.05.

Main Effects and Interactions: The trial is a  $2^4$  full factorial design (4 factors with 2 levels each), resulting in 16 experimental conditions. **Importantly, this is not a 16-arm randomized control trial:** in factorial designs, subjects are “recycled,” allowing for the N per level (e.g. subjects randomized to loss-framing) to be the relevant value rather than the n per experimental condition.(Collins 2018) Effect coding will be used to represent each factor level (e.g. -1 for loss-framed and +1 for gain-framed).(Collins, Dziak et al. 2014) Effect coding allows effect estimates to be uncorrelated when the factorial study is balanced, which allows hypothesis tests to be independent.(Collins 2018) With effect coding, beta coefficient standard errors are equal, so in a balanced design, the power to detect each coefficient is the same.

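### Sections 6.4 and 8.1.1 give conflicting covariate rules, and entering covariates on chance imbalance forgoes the precision of always adjusting for run-in MVPA

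*Combined protocol and SAP*

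**What the plan says.** Five places bear on which covariates enter the models.

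- **Section 8.1.1 (Randomization).** If key covariates differ across component levels at baseline, "we will consider including those variables as covariates in our statistical models". Age, sex and baseline activity are the examples. No test, threshold or decision-maker is named.
- **Section 6.4 (Control of Bias and Confounding).** "Multivariable models will adjust for covariates including age, sex, race, ethnicity, disease type (prediabetes versus diabetes), baseline laboratory values, anthropometrics", and the list goes on to baseline activity. This is unconditional and contains all three of the Section 8.1.1 examples. For motivation and delay discounting it adds a second trigger: "If imbalanced across components, these measures will be included in multivariable models".
- **Section 6.3 (Exploratory Measures).** Discounting, relative autonomy, healthy eating and smartphone steps are collected for use as covariates, with no imbalance condition.
- **Section 6.5.3, Table 1 (Analysis plan).** The primary outcome gets ANOVA/ANCOVA without a covariate list. Healthy Eating Index, discounting and relative autonomy are each labelled ANCOVA covariates.
- **Section 6.5.1.** The primary analysis is described as an ANOVA on change in MVPA, with no covariates. Section 6.1 instead defines the endpoint as the week-12 mean.

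The power table in Section 6.6 shows no covariate.

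**The concern.** Age, sex and baseline activity are optional and conditional in one section and compulsory in another. Motivation and discounting are conditional in Section 6.4 but unconditional in Section 6.3 and Table 1. Two competent statisticians could fit different primary models to the same data and each claim to follow the plan.

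The trigger also uses the wrong criterion. Under correct randomisation a baseline difference between factor levels is chance and says nothing about whether the variable matters. A covariate earns its place by predicting the outcome. Second-week run-in MVPA is the obvious candidate, and it is collected on everyone who is randomised. A rule that admits it only when it happens to look imbalanced leaves it out of most trials.

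What is at stake is precision, and a primary model that is not fixed before the data are seen.

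**Working it through.** **Inputs from the plan.** Size and alpha: "Using a sample size of 64, 4 factors (n=16/factor, n=4/experimental condition), and two-sided alpha = 0.05" (Section 6.6). Effect: "we will have at least 80% power to detect a 15-minute change in MVPA assuming a standard deviation of 20 minutes" (Section 6.6). With effect coding the standardised coefficient is (15/2)/20 = 0.375, printed as 0.38. The full 2⁴ model has 16 parameters, so residual df = 64 − 16 = 48.

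**Assumptions, because the documents give no figure.** ρ from 0 to 0.7. The trigger is p<0.05 for run-in MVPA on any of the four factors. Data are normal and the design is balanced.

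**Step 1: the plan's own figure.** λ = 64 × 0.375² = 9. Non-central F on 1 and 48 df gives 0.836 (plan: 0.84). At alpha 0.1 it gives 0.905 (plan: 0.91). The stated power reproduces without covariates.

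**Step 2: always adjusting.** With p covariates, one of which correlates ρ with the outcome and the rest not at all, λ = 9/(1 − ρ²) × (47 − p)/47 on 48 − p df. For p = 1:

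- ρ = 0: λ = 8.81, power 0.83
- ρ = 0.3: λ = 9.68, power 0.86
- ρ = 0.5: λ = 11.74, power 0.92
- ρ = 0.7: λ = 17.27, power 0.98

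**Step 3: the trigger.** Under the assumed test, run-in MVPA enters with probability 1 − 0.95⁴ = 0.185. Simulation of 64-person balanced trials gave entry rates of 17% to 21%. Ranges below cover separate simulation runs and, in the last column, the Step 2 formula. The lower trigger values come from runs in which age and sex were candidates too.

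| ρ (week-12 outcome) | Trigger | Run-in MVPA always in |
|---|---|---|
| 0 | 0.83–0.84 | 0.83–0.84 |
| 0.3 | 0.84–0.85 | 0.86–0.87 |
| 0.5 | 0.84–0.86 | 0.92 |
| 0.7 | 0.86–0.88 | 0.98–0.99 |

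**Step 4: if the outcome is change.** Take SD 20 as the SD of change and assume equal variances at both times. Adjusting for baseline multiplies the residual variance by (1 − ρ²)/[2(1 − ρ)] = (1 + ρ)/2. Then λ = 9 × 2/(1 + ρ) × 46/47:

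- ρ = 0.3: λ = 13.55, power 0.95
- ρ = 0.5: λ = 11.74, power 0.92
- ρ = 0.7: λ = 10.36, power 0.88

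Unadjusted power is 0.84. Simulated power with the trigger was 0.86, 0.85 and 0.83 to 0.84. Here the gain from adjusting is largest when ρ is low.

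**Step 5: type I error.** With no true effect, simulated rejection rates were between 0.04 and 0.05 under the trigger and about 0.05 when always adjusting for run-in MVPA. There is no inflation.

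**Step 6: the Section 6.4 list.** It names eight headings. Taking one term each for age, sex, race, ethnicity, disease type, BMI-Z and baseline activity, and eight for the laboratory tests in Table 1, gives 7 + 8 = 15. Relative autonomy and discounting make 17. At p = 16 the list uses 16 of 48 residual df, one third, and the standard error grows by √(47/31) = 1.23 before any prognostic gain. If only run-in MVPA is prognostic (week-12 outcome):

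| ρ | λ on 32 df | Power |
|---|---|---|
| 0 | 5.94 | 0.66 |
| 0.3 | 6.52 | 0.70 |
| 0.5 | 7.91 | 0.78 |
| 0.7 | 11.64 | 0.91 |

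Read as eight terms, with one laboratory value per model, ρ = 0.5 gives λ = 12 × 39/47 = 9.96 on 40 df and power 0.87. In simulation at ρ = 0.5, sixteen terms overtook a fixed list of three only when the extra terms explained roughly 25% to 30% more outcome variance (0.88 v 0.91 at 20%, 0.95 v 0.92 at 30%).

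**The case against.** **The size of the loss is conditional.** Run-in MVPA is capped at 30 minutes per day by the eligibility rule (Section 3.1.3), which may hold ρ down. For the week-12 outcome the trigger then costs little: nothing at ρ = 0 and one or two points at 0.3. This stands for that outcome. It does not carry over to the change outcome of Section 6.5.1, where low ρ is where adjustment gains most.

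**The p<0.05 trigger is an assumption.** Section 8.1.1 speaks only of considering covariates, so entry is discretionary. A looser threshold would admit run-in MVPA more often and shrink the loss. This stands, but a discretionary rule is less reproducible than a numerical one. A reader might also multiply five trigger variables by four factors and quote a 64% chance (1 − 0.95²⁰) that something triggers. That merges two separate triggers under a test that neither section states, and it is not the chance that the prognostic variable enters.

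**Section 6.4 may not govern the primary analysis.** Its multivariable models are not tied to the primary ANOVA; they could be the mixed models of Section 6.5.1 or the ANCOVA option in Table 1. This stands. A reader might infer that the plan puts about 16 adjusters into the primary model and so falls to about two-thirds power. The text lists eight headings, not 16 terms, and the low figure needs ρ = 0 for a list that itself contains baseline activity.

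**Analysis is blinded to factor labels (Section 8.1.2).** That limits steering toward a preferred result, but it does not fix the covariate set.

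**Conclusion.** The point holds in a limited form. The covariate rules conflict on the same variables, no primary covariate set is fixed, and entry on chance imbalance is inferior to always including run-in MVPA.

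Under the stated assumptions, the trigger gives up about 2 points of power at ρ = 0.3, about 6 at 0.5 and about 11 at 0.7 for the week-12 outcome, and nothing at ρ = 0. For the change outcome with equal variances, always adjusting gives about 0.95, 0.92 and 0.88 at those three correlations, against 0.84 unadjusted.

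Two stronger conclusions are tempting and are not supported. The trigger does not take power materially below the stated 0.84, because that figure assumes no covariates at all; what is lost is a gain. Nor does the trigger produce false positives, since simulated type I error was at or slightly below nominal.

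The long list is a separate and more conditional risk. It falls below 80% power for ρ up to about 0.5 only if it is expanded to about 15 to 17 terms, applied to the primary model, and its other terms are not prognostic.

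**What to change.** - Delete the imbalance triggers in Sections 6.4 and 8.1.1.
- State one primary ANCOVA that always includes second-week run-in MVPA, with at most age, sex and disease type added, whatever the observed balance. For other outcomes, use that outcome's own baseline value. With baseline in the model, the factor effects are the same whether the response is the week-12 value or the change, so this also removes most of the tension between Sections 6.1 and 6.5.1.
- Align Sections 6.3, 6.4, 6.5.1, 8.1.1 and Table 1 (Analysis plan) with that model. Editing only 6.4 and 8.1.1 would leave other covariate lists standing.
- Move all other covariates to one labelled sensitivity model. Flag there that the dietary recalls (intervention weeks 1–2, Section 5.1.6) and smartphone steps (weekly during the intervention, Section 5.1.9) are measured after randomisation.

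The cost is wording plus one to four residual df. If no covariate is prognostic, one covariate takes power from 0.84 to 0.83. Four take it to 0.80 (λ = 9 × 43/47 = 8.23 on 44 df; standard error up by √(47/43) − 1 = 4.5%). With four covariates and ρ = 0.3 for run-in MVPA alone, power is again about 0.84 (λ = 9.05), so the three additions should be kept only if they are expected to predict MVPA.
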